33. Follow up period: Patients should be evaluated for adverse events up to 60 days after last dose of study treatment. Patients continuing to experience toxicity at this point will continue to be followed at least every 4 weeks until resolution or determination, in the clinical judgment of the Investigator, that no further improvement is expected. Immunogenicity (ADA) samples should be collected beyond 28 days for patients who are positive for ADA (Refer to Footnote 27). During the follow-up phase, Immunogenicity (ADA) samples should be collected at the same time as disease assessments are being performed until ADA levels return to baseline or until the patient enters the survival follow phase. Thereafter, patients whose disease has not progressed at the end of treatment will enter into disease follow-up. During this follow-up period, patients will have disease assessments performed every 16 weeks (± 1 week). Once patients have exhibited disease progression, they will enter into survival follow-up for assessment of survival only. A new anti-cancer therapy will be reported on the CRF. Survival follow-up will be conducted within 12 weeks (+/- 4 weeks) from the last survival follow-up for up to 2 years from first dose of study treatment for the last enrolled patient (telephone calls acceptable).
34. For infusion reactions to rituximab where a partial dose (<50% of the full dose) is administered, either the Day -7 dose OR the Day 0 administration of Cycle 1 and the associated procedures may be repeated one time based on the rituximab label guidelines, local practice, and eligibility for retreatment as detailed in Section 5.4.
35. For patients continuing on study beyond 8 cycles of therapy, continued treatment will be on a reduced visit schedule (Day 1 of each cycle), or as clinically indicated, until disease progression, unacceptable toxicity, or withdrawal of consent up to a maximum of 2 years from the first dose of study drug.

CCI

Table 5. Schedule of Activities for Expansion Cohorts (Portions A and B)

Protocol Activity (Cycle Day relative to PF-05082566 dosing)	Screen ¹	CYCLE 1					CYCLE ≥2	End of Treatment ²	Follow up ³
	Within 28 days prior to randomization OR enrollment	Day -7 ⁴ (Portion B Only)	Day 0 ⁴ (Portion B Only)	Day 1	Day 7 (Portion B Only)	Day 14 (Portion B Only)	Day 1 (±) 2		
Informed Consent	X								
Tumor History ⁵	X								
Medical History ⁶	X								
Physical Examination ⁷	X	X		X			X	X	
ECOG Performance Status ⁸	X	X		X			X	X	

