15. Serum/Urine Pregnancy Test: For female patients of childbearing potential, who do not fit for the definition of “female patients of nonchildbearing potential” in inclusion criterion 11, a serum or urine pregnancy test, with sensitivity of at least 25 mIU/mL, will be performed on 2 occasions prior to starting administration of study treatment: once at the start of screening and once at the baseline visit, immediately before administration of the first dose of study treatment. Pregnancy tests will also be routinely repeated at every cycle during the active treatment period, at the end of study therapy and additionally whenever one menstrual cycle is missed or when potential pregnancy is otherwise suspected. Additional pregnancy tests may also be undertaken if requested by institutional review board/ethics committee (IRB/ECs) or if required by local regulations.
16. Endocrine function assessment: thyroid function testing should be performed at screening, on Cycle 3 Day 1, every 12 week thereafter, and at the end of treatment; ACTH and cortisol levels should be assessed in cases of suspected hypoadrenalism or hypopituitarism. See [Table 8](#) for Laboratory Tests list.
17. LVEF assessment: measurement of ejection fraction by echocardiogram (ECHO), multigated acquisition (MUGA) scan, or an equivalent methodology.
18. Registration: In the randomized cohorts of Portion A for patients with advanced melanoma, patient enrollment and assignment of PF-05082566 dose level is managed through the use of an interactive response technology (IRT) system. In the non-randomized cohorts of Portion A and Portion B patient number and dose level allocation is operated by Pfizer.
19. PF-05082566 administration: PF-05082566 will be administered once every 4 weeks as a 1 hour (-5/+15 min) IV infusion (each cycle =28 days). For the randomized cohorts in Portion A patients will be randomized 2:1:1 to the 0.6 mg/kg, 1.2 mg/kg and 0.24 mg/kg dose levels of PF-05082566, respectively. Patients enrolled in the non-randomized cohorts of Portion A and Portion B will receive either the 1.2 mg/kg or 0.24 mg/kg dose level of PF-05082566.
20. Rituximab administration (Portion B only): rituximab (375 mg/m²) will be administered as an IV infusion once weekly for 4 doses during Cycle 1 starting on Cycle 1 Day -7. Refer to [Section 5.4](#) of the protocol on administration and management of infusion related AEs and to the rituximab package insert.

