21. In Portion B only, patients may have received additional doses of rituximab (375 mg/m²) starting at Cycle 4, in accord with the local and institutional Standard of Care, and at the discretion of the investigator. A single dose of rituximab will be administered on Day 0 starting on Cycle 4 and will be repeated every 2 cycles up to a maximum of 4 additional doses (up to Cycle 10 Day 0).
22. Tumor Assessments: Tumor assessments will include all known or suspected disease sites. Imaging may include chest, abdomen and pelvis CT or MRI scans. Brain scans and will be performed at baseline for patients with CNS disease or if disease is suspected, and on study as appropriate to follow disease. Baseline CNS imaging is not required unless to confirm stability of existing CNS metastases or for symptomatic patients to rule out CNS metastases. Bone scans will be performed at baseline if disease is suspected only for patients enrolled in Portion A, and on study (every 16 weeks ±1 week) as appropriate to follow disease. CT or MRI scans to be done once every 8 weeks (±1 week) for the first 10 months on study treatment, then subsequently every 16 weeks (±1 week) until objective disease progression. Confirmation of response (CR/PR) should be done at least 4 weeks after the initial response, per RECIST v1.1 CCI. Confirmation of response (CR/PR) is not required for patients with NHL per Cheson 2007 response criteria. Tumor assessment should be repeated at the end of treatment visit if more than 6 weeks have passed since the last evaluation. Patients whose disease has not progressed at the end of treatment will enter into disease follow-up. During this follow-up period, patients will have disease assessments performed every 16 weeks (±1 week). All radiographic images from patients with rituximab refractory FL enrolled in the expansion cohorts Portion B must be collected and sent to a central radiology laboratory for potential future independent review. See the study manual for more details

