- Blood for PF-05082566 Pharmacokinetics: Blood samples will be collected for at least 5 patients in each dose expansion cohort (dosed with PF-05082566 at 1.2 mg/kg OR 0.24 mg/kg) with the following schedule: during Cycle 1 on (a) Day 1 at pre-dose, end of infusion, and at 2, 6 and 24 hr post start of infusion; (b) 1 sample on Days 7 and 14, respectively. During Cycle 2 and Cycle 3 on (c) Day 1 at pre-dose, end of infusion. During Cycle 4 on (d) Day 1 at pre-dose, end of infusion, and at 2, 6 and 24 hr post start of infusion; (e) 1 sample on Days 7 and 14, respectively. After Cycle 4, PK samples will be collected on Day 1 at pre-dose every four cycles. For the remaining patients, PK samples will be collected on Day 1 of Cycles 1 to 4 at pre-dose and end of infusion. After Cycle 4, PK samples will be collected on Day 1 at pre-dose every 4 cycles. A PK sample should be collected at the End of Treatment assessment.
- Blood for Rituximab Pharmacokinetics (NOTE: All days are numbered relative to PF-05082566 dosing): Blood samples will be collected for at least 5 patients enrolled in the dose expansion cohort dosed with PF-05082566 at 1.2 mg/kg on (a) Day -7) and Day (0) at pre- dose and end of infusion of rituximab (b) on Cycle 1 Day 1 at 2 and 24 post start of infusion of PF-05082566; (c) on Cycle 1 Day 7 and Day 14 at pre-dose and end of infusion of rituximab; (f) 1 sample on Cycle 2 Day 1 before the dose of PF-05082566; PK samples should be collected at the End of treatment/Withdrawal assessment day. For the remaining patients, PK samples for rituximab will NOT be collected. Note that whenever rituximab PK samples are collected on days when PF-05082566 PK samples are collected, they should be time matched to avoid multiple sticks.
- Blood for PF-05082566 Immunogenicity (ADA) testing: Blood for immunogenicity testing will be collected at a) Day 1 at pre-dose from Cycle 1 to Cycle 4 b) after Cycle 4, ADA samples will be collected on Day 1 at pre-dose every four cycles (Cycle 8, Cycle 12, etc.). Immunogenicity samples should be collected at the End of Treatment assessment day.
- Blood for Rituximab Immunogenicity (ADA) testing (NOTE: All days are numbered relative to PF-05082566 dosing): Blood for immunogenicity testing will be collected at a) Cycle 1 On Day (-7), Day 0, Day 7 and Day 14 prior to the dosing of rituximab; (b) On Cycle 2 Day 1 prior to the dosing of PF-05082566; (d) end of treatment.

Table 8 Safety Laboratory Tests

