3.3.2. Portion B (PF-05082566 + Rituximab)

Safety of the single agent within the first 3 cohorts of Portion A will trigger the initiation of Portion B. The initiation of Portion B may occur after all patients in the single agent 0.06 mg/kg cohort have completed Cycle 1 and received their second dose. Enrollment will then begin with PF-05082566 at a dose of 0.03 mg/kg and escalating at the same dose intervals as listed for Portion A. PF-05082566 will be given to patients IV (every 4 weeks) in combination with rituximab (375 mg/m², every week during Cycle 1). Patients clinically benefiting from study treatment without unacceptable toxicity, objective disease progression, or withdrawal of consent will be given the opportunity to continue treatment up to a

maximum of 2 years from the first dose of study drug. The first dose of PF-05082566 will be given approximately 24 hours after the second weekly, full dose of rituximab (defined as either the planned dose or in the case of infusion reactions, at least 50% of planned rituximab dose; see [Section 5](#) for details). For the first cohort (PF-05082566 given at 0.03 mg/kg) there will be a minimum 7 day window between the first dose of PF-05082566 for a patient and the first dose of rituximab for the next patient.

For all subsequent dose escalation/de-escalation cohorts, up to 0.6 mg/kg, a minimum 72 hour window will apply between the first dose of PF-05082566 for a patient and the first dose of rituximab for the next patient in the same cohort. Updated safety information in patients indicates that PF-05082566 infusion has thus far not resulted in clinically significant infusion reactions. Therefore, there will be no longer be a waiting period between patients in the same dose cohort and in dose expansion cohorts.

The proposed doses and schedule may be reconsidered and amended during the study based on the emerging safety and PK **CCl** data.

See the additional rules below for more details regarding dose escalation. Patients in Portion B will be replaced only if they discontinue prior to receiving the first dose of PF-05082566.

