PF-05082566 will be administered at 2 planned dose escalation levels (5.0 mg/kg and 10 mg/kg) by IV infusion of 1 hour (-5/+15 min) every 4 weeks. Each patient will initially receive the first dose on Cycle 1 Day 1 with a 28-day observation period. Cycle 2 Day 1 will start on Day 29. After completion of Cycle 2, patients will be asked to sign an additional consent document for confirmation of the patient's willingness to continue participation in this study before starting Cycle 3. Lower dose levels, as described above for Portion A, may be explored at any time during the study if this is clinically and scientifically warranted based on the emerging safety data in Japanese patients. Study centers will receive a notification if additional dose levels are explored.

Portion B:

PF-05082566 will be administered by IV infusion of 1 hour (-5/+15 min) every four weeks at dose levels as shown for Portion A, with the exception that the Portion B dose escalation starts at 0.03 mg/kg.

In the expansion cohort, patients enrolled in Portion B will receive a dose of PF-05082566 at 0.24 mg/kg or 1.2 mg/kg in combination with 375 mg/m² rituximab. If a PF-05082566 dose reduction is required due to the PF-05082566-related toxicity, this may be allowed as an alternative to discontinuation of treatment. No dose reduction is allowed for patients treated at the 0.24 mg/kg dose level. See [Section 5.4.4](#) for details.

Rituximab will be administered in Cycle 1 at a fixed dose of 375 mg/m², once per week for a total of 4 weeks. The first dose of rituximab will be administered on Cycle 1 Day (-7) followed by the second dose a week later on Day (0).

The first dose of PF-05082566 will be given approximately 24 hours after the second weekly, full dose of rituximab (Cycle 1 Day 1). This allows for the observance of any potential reactions to rituximab treatment prior to the initiation of PF-05082566 dosing. In this study, full dose of rituximab is defined as either the planned dose, or for those patients who develop an infusion reaction, as at least 50% of the planned dose. Continuation with protocol activities as scheduled, following administration of less than the planned rituximab dose, requires confirmation of dose acceptability from the Sponsor.

The proposed schedule and duration of infusion may be reconsidered and amended during the study based on the emerging safety and PK **CCI** data.

Duration of Treatment

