5.4. Administration

Patients will receive doses of PF-05082566 IV once every 4weeks (1 cycle). A cycle is defined as the time from the Day 1 dose to the next Day 1 dose. If there are no treatment delays, a cycle will be 4 weeks in duration.

Premedication is recommended for all patients, and may include an antihistamine, an anti-inflammatory agent, or a pain reliever.

The duration of infusion is 1 hour (-5/+15 minutes). The infusion rate should be reduced or interrupted in the case of symptoms of infusion reaction, and symptomatic treatment administered. The infusion may be continued at one-half the previous rate upon improvement of symptoms. If symptoms persist or worsen, the infusion should be discontinued permanently.

Patients on Portion B of the study will receive doses of rituximab IV once every week for the first cycle of treatment at a fixed dose of 375 mg/m². Initiation of PF-05082566 will commence approximately 24 hours after the second weekly on study full dose of rituximab has been administered. For additional details about the administration of rituximab, refer to rituximab package insert.

Medication errors may result in this study from the administration or consumption of the wrong product, by the wrong patient, at the wrong time, or at the wrong dose strength, or administration of a study drug at the wrong study visit day. Such medication errors occurring to a study participant are to be captured on the medication error case report form (CRF) which is a specific version of the adverse event (AE) page and on the SAE form when appropriate. In the event of medication dosing error, the sponsor should be notified immediately.

Medication errors are reportable irrespective of the presence of an associated AE/SAE, including:

- Medication errors involving patient exposure to the investigational product.
- Potential medication errors or uses outside of what is foreseen in the protocol that do or do not involve the participating patient.

Whether or not the medication error is accompanied by an AE, as determined by the investigator, the medication error is captured on the medication error version of the adverse event (AE) page and, if applicable, any associated AE(s) are captured on an AE) CRF page.

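### Table 5 footnote 21 still reads as an instruction to give rituximab after Cycle 1, and the SAP dose-delay formula would record an on-schedule later dose as 49 or 63 days late (minor)

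*Protocol*

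**What the plan says.** **Protocol.** Table 5 covers the expansion cohorts. Footnote 20 says that rituximab 375 mg/m² "will be administered as an IV infusion once weekly for 4 doses during Cycle 1 starting on Cycle 1 Day -7". Footnote 21, for Portion B only, begins by saying that "patients may have received additional doses of rituximab" from Cycle 4, according to local standard of care and investigator discretion. It continues: "A single dose of rituximab will be administered on Day 0 starting on Cycle 4 and will be repeated every 2 cycles", with at most four extra doses, the last on Cycle 10 Day 0.

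The body of the protocol gives one schedule:
- Section 3.3.2: "every week during Cycle 1".
- Section 5: "once per week for a total of 4 weeks", in Cycle 1.
- Section 5.4: "once every week for the first cycle of treatment".

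The Table 5 header has a Day 0 column under Cycle 1 only; from Cycle 2 on, the only visit is Day 1. Section 6 sends sites to Tables 1 to 7 for treatment-period procedures.

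**SAP.** Section 6.5.3 says that its derivations assume rituximab on Days -7, 0, 7 and 14 of the first cycle. Section 6.5.3.2 sums all rituximab received, fixes the intended duration at 4 weeks, and takes 375 × 4 mg/m² as the intended dose per 4-week cycle. Section 6.5.3.4 defines delay as the actual minus the planned interval between consecutive doses. Its rituximab formula then subtracts 7 days from the gap before every dose after the first.

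**The concern.** The two sentences of footnote 21 do not agree in tense. The first records what some patients may have been given; the second tells the reader what will be given. Because the schedule tables are the working reference for sites, a site could read the second sentence as a current dosing instruction for Portion B and give up to four infusions that Sections 3.3.2, 5 and 5.4 do not plan. Rituximab infusions carry the reaction risks described in Section 5.4. Under that section, an infusion interrupted after Cycle 1 Day 1 that cannot be completed within 24 hours ends all study treatment, including PF-05082566.

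The footnote also allows that some patients were re-treated, and the SAP has no rule for their later doses. The delay table is one that the SAP commits to producing, using each patient's longest delay. One on-time re-treatment dose could therefore move a patient from no delay to the longest-delay category, depending on which sentence of 6.5.3.4 is programmed.

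**Working it through.** **Inputs.** Cycle length 28 days and rituximab 375 mg/m² (Table 5 footnotes 19 and 20). Planned doses on Cycle 1 Days -7, 0, 7 and 14 (SAP 6.5.3). Extra doses on Day 0 of Cycles 4, 6, 8 and 10 (footnote 21). All patients are taken to be dosed exactly on schedule.

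**Calendar.** In days from Cycle 1 Day 0, the planned doses fall at -7, 0, 7 and 14. Day 0 of Cycle c falls at 28 × (c - 1), so the extra doses fall at 84, 140, 196 and 252. That is four doses, which matches the footnote's maximum.

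**The SAP's own case first (four doses).**
- Cumulative dose 4 × 375 = 1500 mg/m², the intended 375 × 4. RDI = 1500/1500 = 100%.
- Exposure duration (last - first + 7)/7 = (14 + 7 + 7)/7 = 4 weeks.
- Each delay is 7 - 7 = 0 days.
- Counting Day -7 as study day 1, the first PF-05082566 dose is on study day 9, the offset in 6.5.3.4.

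The formulas are consistent for the schedule that they assume.

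**Delay for a re-treated patient (6.5.3.4).**

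| Dose | Actual gap (days) | Planned gap, footnote 21 | Delay by the definition | Delay by the formula (gap - 7) |
|---|---|---|---|---|
| Cycle 4 Day 0 | 84 - 14 = 70 | 70 | 0 | 63 |
| Cycle 6 Day 0 | 140 - 84 = 56 | 56 | 0 | 49 |
| Cycle 8 Day 0 | 196 - 140 = 56 | 56 | 0 | 49 |
| Cycle 10 Day 0 | 252 - 196 = 56 | 56 | 0 | 49 |

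By the formula, every re-treated patient lands in the category of 7 days or more. By the definition, none does.

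**Dose intensity for a re-treated patient (6.5.3.2).** Actual intensity = cumulative dose/(4/4), and RDI = 100 × actual intensity/1500.

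| Extra doses | mg/m² per 4-week cycle | RDI | Exposure duration (weeks) |
|---|---|---|---|
| 1 | 5 × 375 = 1875 | 125% | (84 + 7 + 7)/7 = 14 |
| 2 | 6 × 375 = 2250 | 150% | (140 + 7 + 7)/7 = 22 |
| 3 | 7 × 375 = 2625 | 175% | (196 + 7 + 7)/7 = 30 |
| 4 | 8 × 375 = 3000 | 200% | (252 + 7 + 7)/7 = 38 |

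The RDI correctly shows drug beyond the planned 1500 mg/m². The rate label is what misleads. The largest amount given in any 4 weeks is the 1500 mg/m² of Cycle 1. After Cycle 1 the doses are 56 days apart, so no 4-week period holds more than one dose of 375 mg/m².

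**The case against.** Read whole, footnote 21 is most naturally a retained description: its second sentence sets out the schedule of the doses mentioned in its first. The Amendment 9 summary, taken only as evidence of intent, says that this later dosing was taken out. Footnote 20, three body sections, the SAP treatment-group labels and the visit grid all point to Cycle 1 only. So the footnote is probably a drafting remnant, and most sites would not act on it. That stands, and it lowers the severity. It does not change the wording of the second sentence, which is in the future tense and sits in a table that sites are told to follow.

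On the SAP, the objection is that 6.5.3 states its Cycle 1 assumption openly, so applying the 7-day formula to later doses would be a programming error. This stands in part. The formula is nonetheless written for every dose after the first, and it disagrees with the definition in its own section. Two programmers could follow the text and produce different tables.

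On dose intensity the objection largely stands. An RDI above 100% is informative, and 6.5.3 says only that exposure may be summarized this way. Cutting the extra doses out of the RDI would remove a useful signal.

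Table 7 does not help either side: rituximab sampling that stops at Cycle 2 Day 1, apart from End of Treatment, is compatible with later doses being given or not.

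**Conclusion.** The point holds as a minor one. Footnote 21 conflicts with footnote 20 and Sections 3.3.2, 5 and 5.4 in current text, and the rituximab delay formula conflicts with its own definition by 63 or 49 days per on-schedule later dose. Those figures assume exact 28-day cycles and dosing on the footnote's schedule.

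A reader might infer three stronger things that the documents do not support:
- **That later rituximab is scheduled without limit.** The footnote's text names no date, amendment or cohort beyond Portion B. The rituximab row of Table 5 is missing from the available text, however, so a limit shown there cannot be excluded.
- **That patients were in fact re-treated.** The footnote says only that they may have been. By September 2016 the Portion B expansion had enrolled 10 FL and 4 DLBCL patients (Section 3.1.2); how many, if any, had extra rituximab is not stated.
- **That the trial's results are affected.** ORR, DLT and adverse-event analyses do not use these formulas, and the documents do not allow any effect of re-treatment on ORR to be determined.

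**What to change.** **Protocol, Table 5 footnote 21.** Limit it to patients dosed under earlier amendments, put the second sentence in the past tense, and state that no rituximab is given after Cycle 1.

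**SAP 6.5.3.4.** Apply the 7-day rituximab formula only to the four weekly Cycle 1 doses, and list any later doses separately.

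**SAP 6.5.3.2.** Keep the cumulative dose and the RDI as they are, so that a value above 100% still signals extra drug. Flag patients given rituximab after Cycle 1, with a note that for them the figure per 4-week cycle is not a rate actually received.

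**Cost.** One footnote, one clause in 6.5.3.4, one note in 6.5.3.2, one patient flag and one listing. All of it comes from dose dates already collected, and no endpoint analysis changes.
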